**Proprietary confidential information.**

**© 2016 Boehringer Ingelheim International GmbH or one or more of its affiliated companies. All rights reserved.**

This document may not - in full or in part - be passed on, reproduced, published or otherwise used without prior written permission.

Number of global amendment	4
Date of CTP revision	01 Oct 2015
EudraCT number	2010-024456-29
BI Trial number	1270.2
BI Investigational Product(s)	BI 836826
Title of protocol	A Phase I, Open-Label, Dose-Escalation Trial with BI 836826 in Patients with Relapsed or Refractory non-Hodgkin Lymphoma of B cell Origin
To be implemented only after approval of the IRB/IEC/Competent Authorities	
To be implemented immediately in order to eliminate hazard – IRB / IEC / Competent Authority to be notified of change with request for approval	
Can be implemented without IRB/IEC/ Competent Authority approval as changes involve logistical or administrative aspects only	
Section to be changed	
Change 1: Trial Responsibility for Trial Clinical Monitor changed from to
 
Change 2: Synopsis – No of patients changed from approx. 80 to approx. 66, no of entered patients changed from approx. 70 to approx. 53, treatment was modified in order to display the required number of Korean patients for both treatment dosages (50 and 75mg)
 
Change 3: Section 1.2 DRUG PROFILE – currently performed trials in B-NHL malignancies and chronic lymphocytic leukemia were added.

Proprietary confidential information.

© 2016 Boehringer Ingelheim International GmbH or one or more of its affiliated companies. All rights reserved.

This document may not - in full or in part - be passed on, reproduced, published or otherwise used without prior written permission.

Number of global amendment	
	
4
 
Change 4: Section 2.2 TRIAL OBJECTIVES – addition of results, which were generated in this trial and analysed after an interim database lock, to display changed recruitment expectation based on the safety analyses.
 
Change 5: 2-3 BENEFIT-RISK ASSESSMENT – further in vitro, in vivo and first in human experiences with treatment of BI 836826 were added. Furthermore the risk of increased neutropenia was added and the information, that infections should be treated in an early stage.
 
Change 6: Section 3.2 DISCUSSION OF TRIAL DESIGN, INCLUDING THE CHOICE OF CONTROL GROUP – modified trial design concerning inclusion of Asian patients.
 
Change 7: Section 3.3.3 EXCLUSION CRITERIA – criterion 26 was deleted as already reflected by criterion #4.
 
Change 8: Section 4.1.1 IDENTITY OF BI INVESTIGATIONAL PRODUCT AND COMPARATOR PRODUCT – Exact volume of infusion was deleted and instead a reference to section 4.1.6 with detailed explanation included.
 
Change 9: Section 4.1.3 SELECTION OF DOSES IN THE TRIAL – MTD doses as examined in Caucasian patients was added and the new possible doses for Asian patients added.
 
Change 10: Section 4.1.4.3 New section added ‘MANAGEMENT OF INFECTIONS’ to establish a standardized process in case of infections due to additional safety precaution.
 
Change 11: Section 4.1.4.4 CONTINUATION OF TREATMENT DURING A COURSE - Criteria for re-start of trial medication were expanded by two criteria (‘no active infection’ and ‘no evidence of progressive disease’).

Proprietary confidential information.

© 2016 Boehringer Ingelheim International GmbH or one or more of its affiliated companies. All rights reserved.

This document may not - in full or in part - be passed on, reproduced, published or otherwise used without prior written permission.

Number of global amendment	4
	
Change 12: Section 4.2.1.2 SUPPORTIVE CARE – infections were added in order to take supportive care infections.
 
Change 13: Section 4.2.1.2.1 ANTIBIOTICS AND ANTIVIRALS – more detailed procedure for how to treat infections was added.
 
Change 14: Section 4.2.2.1 RESTRICTIONS REGARDING CONCOMITANT TREATMENT – typo was corrected.
 
Change 15: Section 5.2.2.2 ADVERSE EVENT AND SERIOUS ADVERSE EVENT REPORTING – According to internal guidelines, clarification of SAE follow-up was included.
 
Change 16: Section 5.5.3 ANALYTICAL DETERMINATION – description of the analysation method was corrected.
 
Change 18: Section 7.3.2.1 TUMOUR SIZE size was deleted
 
Change 19: Section 7.3.2.3 BLOOD COUNTS – complete section was deleted as it will not be followed anymore.
 
Change 20: Section 7.3.2.4 BEST OVERALL RESPONSE - Analysation of CRu was added
 
Change 21: Section 7.3.4. INTERIM ANALYSES – adaptation to reflect the result of the interim analyse with regard to MTD.

**Proprietary confidential information.**

**© 2016 Boehringer Ingelheim International GmbH or one or more of its affiliated companies. All rights reserved.**

This document may not - in full or in part - be passed on, reproduced, published or otherwise used without prior written permission.

Number of global amendment	4	
		Change 23: Section 7.6 DETERMINATION OF SAMPLE SIZE – explanation was added, what is statistical rationale for determination of the chosen sample size.

**Proprietary confidential information.**

**© 2016 Boehringer Ingelheim International GmbH or one or more of its affiliated companies. All rights reserved.**

This document may not - in full or in part - be passed on, reproduced, published or otherwise used without prior written permission.

Number of global amendment	5
Date of CTP revision	13 Apr 2016
EudraCT number	2010-024456-29
BI Trial number	1270.2
BI Investigational Product(s)	BI 836826
Title of protocol	A Phase I, Open-Label, Dose-Escalation Trial with BI 836826 in Patients with Relapsed or Refractory non-Hodgkin Lymphoma of B cell Origin
To be implemented only after approval of the IRB/IEC/Competent Authorities	
To be implemented immediately in order to eliminate hazard – IRB / IEC / Competent Authority to be notified of change with request for approval	
Can be implemented without IRB/IEC/ Competent Authority approval as changes involve logistical or administrative aspects only	
Section to be changed	
Change 1: Section 2.2 Trial Objectives – 'Three out of 4 Korean patients have developed significant toxicities (infections) which lead to the need of exploring a lower dose levels (50 and 75mg) in a designated escalation cohort of Korean patients to further characterize safety and efficacy of BI 836826 (c02337389-01).' This was added to clarify that a new patient in Korea is not part of the expansion cohort.
 
Change 2: Section 2.3 Benefit - Risk Assessment – Percentage of patients with mantle cell lymphoma corrected to 6 (14.6%)
 
Change 3: Section 2.3 Benefit Risk Assessment – 'As a result the enrollment into the trial 1270.2

Proprietary confidential information.

© 2016 Boehringer Ingelheim International GmbH or one or more of its affiliated companies. All rights reserved.

This document may not - in full or in part - be passed on, reproduced, published or otherwise used without prior written permission.

Number of global amendment	5
	
has been halted, and this current amendment is submitted to allow for testing lower dose of 50 and 75mg in Korean patients in an escalation cohort for Asian patients.' This was added to clarify that a new patient in Korea is not part of the expansion cohort.
 
Change 4: Section 3.1 Overall trial design and plan – 'Instead, lower dose escalation cohorts of 50mg and 75 mg will be open to test the safety,...'. This was clarified to stress the escalation status of Korean patients on 50 and 75mg.
 
Change 5: Section 3.3.2 – Clarification of inclusion criteria 3 and 6.
 
Change 6: Section 4.1.4.1.1 Premedication 'Acetaminophen/paracetamol 1000 mg p.o. or a clinically comparable dose, or equivalent' was modified to reflect slight flexibility concerning the dose of paracetamol.
 
Change 7: Section 4.1.4.4 – Correction of neutrophil count in brackets and correction of administrative mistake in former protocol.
 
Change 8: 4.2.2.1 - Correction of administrative mistake in former protocol
 
Change 9: 5.1.2.10 – Correction of mistake in former protocol.

2. LIST OF ABBREVIATION

Term	Definition / description
AE	Adverse event
AESI	Adverse event of special interest
ALB	Albumin
ALKP	Alkaline phosphatase
ALT	Alanine amino transferase
aPTT	Activated artial thromboplastin time
AST	Aspartate amino transferase
ATC	Anatomical, Therapeutic, Chemical classification classification
BAS	Basophils
BMI	Body Mass Index
BRPM	Blinded Report Planning Metting
BSA	Body Surface Area
CA	Calcium
COOMB	Direct antiglobulin test
CR	Complete remission
CRu	Complete remission unconfirmed
CRE	Creatinine
CT	Computer tomography
CTh	Concomitant therapy
CTC	Common Terminology Criteria
CTCAE	Common Terminology Criteria for Adverse Events
CTP	Clinical trial protocol
CTR	Clinical trial report
DBL	Database lock
DILI	Drug-induced liver injury
DLT	Dose limiting toxicity
DM&SM	Boehringer Ingelheim Data Management and Statistics Manual
ECOG	Eastern Cooperative Oncology group
eCRF	Electronic case report form
EMEA	European Agency for the Evaluation of Medicinal Products

Term	Definition / description
EOS	Eosinophils
EoT	End-of-text
FFS	Failure free survival
GLU	Glucose
HCT	Haematocrit
HGB	Haemoglobin
ICH	International Conference on Harmonisation
IGA	Immunoglobulin A
IGG	Immunoglobulin G
IGM	Immunoglobulin M
INR	International normalised ratio of prothrombin time (INR)
IRR	Infusion related reaction
K	Potassium
LDH	Lactate dehydrogenase
LYMPH	Lymphocytes
MedDRA	Medical Dictionary for Regulatory Activities
MONO	Monocytes
MRT	Mean residence time
MTD	Maximum tolerated dose
NA	Sodium
NE	Not evaluable
NEUT	Neutrophils
NHL	Non-Hodgkin Lymphoma
NK cells	Natural Killer cells
OBD	Optimal biological dose
O*C	Oracle Clinical
P	Inorganic phosphate
PD	Progressive disease
PFS	Progression free survival

Term	Definition / description
PLT	Platelets
PR	Partial remission
PRT	Prothrombin time
PT	Preferred term
PV	Protocol violation
RBD	Red blood cell count
RD	Relapsed disease
RET	Reticulocytes
SAE	Serious adverse event
SCR	Screened set
SD	Stable disease
StD	Standard deviation
SOC	System Organ Class
SOP	Standard Operating Procedure
SPD	Sum of products of diameter
TBILI	Total bilirubin
TCM	Trial Clinical Monitor
TLS	Tumour lysis syndrome
ToC	Table of contents
TPRO	Total protein
TS	Treated set
TSAP	Trial statistical analysis plan
WBC	White blood cells

3. INTRODUCTION

As per International Conference of Harmonisation, statistical principles for clinical trials, E9 (ICH E9), the purpose of this document is to provide a more technical and detailed elaboration of the principal features of the analyses described in the clinical trial protocol (CTP), and to include detailed procedures for executing the statistical analysis of the primary and secondary variables and other data.

This trial statistical analysis plan (TSAP) assumes familiarity with the protocol, including protocol amendments. In particular, the TSAP is based on the planned analysis specifications as written in CTP Section 7, “Statistical Methods and Determination of Sample Size”. Therefore, TSAP readers may consult the CTP for more background information on the study, e.g., on study objectives, study design and population, treatments, definition of measurements and variables, planning of sample size, randomisation. This TSAP follows the Boehringer Ingelheim (BI) internal reference ([1](#)).

The primary objective of this trial is to determine the maximum tolerated dose (MTD) of BI 836826 in patients with non-Hodgkin lymphoma (NHL) of B-cell origin. BI 836826 is a new biological entity and the maximum planned single dose is 1400 mg. If the MTD is not reached with this dose, an optimal biological dose (OBD) may be defined instead.

The MTD of BI 836826 was defined as 100 mg in this trial for Caucasian patients. This dose was declared based on safety demonstrated during the dose escalation which was performed in 37 Caucasian patients. The results have been reported in the “CTR – Phase I Safety Analysis Report” ([8](#)).

The planned additional expansion phase enrolled 4 patients (all 4 in Korea). After 3 of these 4 Korean patients developed significant toxicities (ie. infections associated with Grade 4 neutropenia), the protocol was amended for the need of exploring lower dose levels (50 mg and 75 mg) in a designated escalation cohort of Korean patients, with the aim of defining a MTD in Korean patients. Thus, the expansion phase on 100 mg had been stopped. Secondary objectives are the collection of overall safety and anti-tumour efficacy data and the determination of the profile of BI 836826.

In the following, study medication always refers to BI 836826.

SAS® Version 9.2 (or higher) will be used for all analyses.

5. ENDPOINTS

5.1 PRIMARY ENDPOINTS

The primary endpoints of this trial are the MTD and the number of dose limiting toxicities (DLTs) during the MTD evaluation period. Instead of the MTD, an OBD might be defined instead.

Maximum tolerated dose (MTD):

MTD is defined as the highest dose studied for which the incidence of DLTs is no more than 17% (i.e., 1/6 patients) during the MTD evaluation period.

The MTD evaluation period is defined as the time from the first administration of study medication to 7 days after the second administration.

Note that in case of administration of split dose during course 1, both infusions on consecutive Days 1 and 2 of Course 1 are considered as the first administration.

Additionally, all information, including adverse events (AEs) qualifying for a DLT from later times, will be considered in the final determination of the dose recommended for Phase II.

5.2 SECONDARY ENDPOINTS

5.2.1 Key secondary endpoints

Not applicable.

5.2.2 Other Secondary endpoints

Tumour size reduction (indicator lesions, spleen and liver nodules)

Tumour size reduction of indicator lesions, spleen nodules and liver nodules will be analysed separately as secondary endpoints as follows:

Tumour size reduction of indicator lesions will be analysed as secondary endpoint “Best % change from baseline in SPD” from imaging data.

Tumour size reduction of liver nodules will be analysed as secondary endpoint “Best % change from baseline in SPD” from imaging data.

Tumour size reduction of spleen nodules will be analysed as secondary endpoint “Best % change from baseline in SPD” from imaging data. Best overall response (according to investigator assessment):

Response will be assessed according to the Standardized or Revised Response Criteria for Malignant Lymphoma from 1999 ([[R04-1585](#)]). Each patient will be assigned to one of the

following categories:

- complete remission (CR)
- complete remission unconfirmed (CRu)
- partial remission (PR)
- stable disease (SD)
- progressive disease (PD)

Best overall response (CR, CRu, PR, SD, PD in this order) is defined as the best overall response obtained since the start of study treatment. Best overall response will be evaluated in two different ways: first, all responses as documented by the investigator (independent of the assessment procedure) will be evaluated. In a further analysis, only disease evaluations for which imaging data are available in the eCRF will be evaluated. In case PD is captured by the investigator, the response PD will be always considered as PD, independent whether imaging data is available at this timepoint or not. For both evaluations only response assessments prior to any further NHL therapy and until PD will be taken into account. For the calculation of the date of response: if patients would have their examinations contributing to the disease assessment over a number of days, the earliest date of the multiple examinations will be considered.

Progression free survival (PFS):

PFS is defined as the time from first administration of study medication until disease progression or death, whatever occurs first.

Patients administered a new additional therapy for NHL recorded in the electronic case report form (eCRF) but not presenting with disease progression before the start of this new NHL therapy will be censored at the date of last response assessment during which the patient was evaluable and did not have the event before the new NHL therapy has started.

Patients not administered another NHL therapy and not presenting with disease progression or death during the trial will be censored at the date of the last response assessment during which the patient was evaluable and did not have the event.

A patient is said to have an evaluable response assessment if a response of CR, CRu, PR, SD or PD has been assigned.

The censoring rules and the applicable dates of outcome for PFS are given in the following table.

Table 5.2.2:1 Derivation rules for progression-free survival

Situation	Outcome (event or censored)	Date of outcome
Baseline and post-baseline disease assessment: disease progression or death without prior additional NHL therapy	Event	Date of first disease progression or death
Baseline and post-baseline disease assessment: disease progression or death and prior additional NHL therapy	Censored	Date of last response assessment before start of new NHL therapy
Baseline and post-baseline disease assessment: No disease progression or death without additional NHL therapy	Censored	Date of last response assessment
Baseline and post-baseline disease assessment: No disease progression or death with additional NHL therapy	Censored	Date of last response assessment before start of new NHL therapy
No baseline or post-baseline disease assessment: without death	Censored	Date of first administration of BI 836826
No baseline or post-baseline disease assessment: death on or before the first planned disease assessment (i.e. at week 4 assessment)	Event	Date of death
No baseline or post-baseline disease assessment: death after first planned disease assessment (i.e. at week 4 assessment)	Censored	Date of first administration of BI 836826

Remark: determination of the response status via disease assessment refers to any disease assessment via imaging or via physical assessment

Progression free survival (PFS) [in days] is therefore the time from first administration of study medication to the earlier date of disease progression or death (minimum date of disease progression or death – date of first administration of study medication + 1).

Progression free survival (PFS) censored [in days] is therefore the time from first administration of study medication to the date of last response assessment (date of last response assessment – date of first administration of study medication + 1).

Failure free survival (FFS):

FFS is defined as the time from first administration of study medication until disease progression or death or start of next NHL therapy.

Patients not administered another NHL therapy and not presenting with disease progression or death during the trial will be censored at the date of the last response assessment during which the patient was evaluable and did not have the event.

The censoring rules and the applicable dates of outcome for FFS are given in the following table.

Table 5.2.2:2 Derivation rules for failure-free survival

Situation	Outcome (event or censored)	Date of outcome
Baseline and post-baseline disease assessment: disease progression or death or start of next NHL therapy	Event	Date of first disease progression or death or start of next NHL therapy
Baseline and post-baseline disease assessment: No disease progression, death or new NHL therapy	Censored	Date of last response assessment
No baseline or post-baseline disease assessment: no death or new NHL therapy	Censored	Date of first administration of BI 836826
No baseline or post-baseline disease assessment: death/next NHL therapy on or before the first planned disease assessment (i.e. week 4 assessment)	Event	Date of death/next NHL therapy
No baseline or post-baseline disease assessment: death/next NHL therapy after the first planned disease assessment (i.e. week 4 assessment)	Censored	Date of first administration of BI 836826

Remark: determination of the response status via disease assessment refers to any disease assessment via imaging or via physical assessment

Failure free survival (FFS) [in days] is therefore the time from first administration of study medication to the earlier of disease progression or death or start date of next NHL therapy. (minimum date of disease progression, death or start of next NHL therapy – date of first administration of study medication + 1).

Failure free survival (FFS) censored [in days] is therefore the time from first administration of study medication to the date of last response assessment (date of last response assessment – date of first administration of study medication + 1).

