#### 5.1.2.4 Failure free survival

Some patients will receive a next line of therapy, although no formal PD may have been diagnosed at the time when the next treatment is indicated according to investigator assessment. In addition to PFS, the failure free survival (FFS) will be calculated to assess this group of patients. FFS is defined as the time from first treatment with BI 836826 until objective disease progression or death or start of next lymphoma therapy.

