### 6.2.3 End of treatment and follow-up period

#### 6.2.3.1 End of treatment

The end of treatment (EOT) visit should be performed if patient and investigator refrain from further therapy at any time during the treatment period. For patients who receive course 3 (12 administrations) at the latest 8 weeks after the last administration of BI 836826. If the patient concludes the trial within a treatment course, the information required to be collected at the EOT visit should be obtained as early as possible, preferably immediately. This includes a CT scan, which may be performed if it is considered clinically indicated, *e.g.* to document disease progression. At the EOT visit assessment of all safety and efficacy parameters should be performed according to flowchart for course 3. The status of the patient at EOT has to be documented, *e.g.* in case the patient has progressive disease the date of first documentation of PD has to be recorded. The reason for the completion of active trial treatment or premature discontinuation of trial, if applicable, has to be stated together with date of last administration of the trial drug. If the patient receives other therapy for lymphoma, the therapy has to be stated by name and date of first treatment. For detail see [flowchart](#) for Course 3.

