#### 6.2.3.2 Follow-up

Follow-up visits will be performed after the EOT visit in case a patient has completed treatment according to protocol or is not eligible for further treatment courses prior to administration of the maximum number of courses. Follow-up will end in case the patient is

- lost to follow-up
- receives new anti-lymphoma therapy
- withdraws consent
- in case the investigator and sponsor agree not to pursue further follow-up visits
- death

Follow-up visits should be performed at 6 weeks intervals or more frequent if appropriate. Follow-up visits should be done at the investigational site, but may be performed by telephone interview in case the patient is unable to visit the investigator. Follow-up visits should be performed up to 6 months after the end of treatment visit. At the last follow-up visit, an end of trial assessment will be performed and documented in the eCRF. For follow-up of patients with adverse events which have not recovered at the last planned follow-up visit please refer to [section 5.2.2.2](#).

The following will be obtained and / or performed (see [flowchart](#) for Course 3):

- Vital signs (see [section 5.2.5.1](#)), weight, physical examination

Proprietary confidential information.

© 2016 Boehringer Ingelheim International GmbH or one or more of its affiliated companies. All rights reserved.

This document may not - in full or in part - be passed on, reproduced, published or otherwise used without prior written permission.

- Disease assessment: clinical assessment of tumour size (lymph nodes, spleen, liver), imaging if applicable
- Changes in concomitant therapies
- Safety laboratory parameters as specified in [section 5.2.3.1](#)
- Adverse events
- CMV monitoring (see [section 5.2.3.3.2](#))
- Lymphocyte typing (see [section 5.2.3.4](#))
- Status of the patient: date of progression (in case, the patient experienced PD) date death (if applicable)
- Treatment with any other anti-lymphoma drug (report start date of treatment and therapy)

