6.6 HANDLING OF MISSING DATA AND OUTLIERS

If not stated otherwise, missing data will not be imputed and remain missing. Potential outliers will be reported and analysed as observed.

Missing or incomplete AE dates are imputed according to BI standards (see [\(5\)](#)).

Missing data and outliers are handled according to 001-MCS-36-472 [\(2\)](#).

If the day of birth is missing, then the imputed days will be the 15th. If start of new NHL therapy date is incomplete (only month given), then the start date will be imputed with the 1st of month unless the first day leads to a date before the stop date of study medication, then the study medication stop date +1 will be imputed. If more than only the day is missing, dates will not be imputed.

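### The last row of SAP Table 5.2.2:2 censors on day 1 a known death or next NHL therapy that the SAP itself defines as a failure-free survival event

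*SAP*

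**What the plan says.** SAP 5.2.2 states: "FFS is defined as the time from first administration of study medication until disease progression or death or start of next NHL therapy". Its event-time formula takes the "minimum date of disease progression, death or start of next NHL therapy", minus the date of first administration, plus one day. Protocol 5.1.2.4 uses the same three event types and explains why FFS stands beside PFS: "Some patients will receive a next line of therapy, although no formal PD may have been diagnosed at the time" when that treatment is indicated.

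On censoring, the SAP text says: "Patients not administered another NHL therapy and not presenting with disease progression or death during the trial will be censored" at the last evaluable response assessment. It then refers to Table 5.2.2:2, which in paraphrase reads:

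| Row | Disease assessments | What happened | Outcome | Date used |
|---|---|---|---|---|
| 1 | Present | Progression, death or next therapy, at any time | Event | Earliest of these |
| 2 | Present | None of these | Censored | Last response assessment |
| 3 | Absent | Neither death nor next therapy | Censored | First administration |
| 4 | Absent | Death or next therapy up to week 4 | Event | Date of death or next therapy |
| 5 | Absent | "death/next NHL therapy after the first planned disease assessment (i.e. week 4 assessment") | Censored | First administration |

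A remark below the table accepts physical as well as imaging assessment. Protocol 7.3.2.4 leaves the censoring details to the SAP, so the table is what will be programmed.

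**The concern.** Row 5 takes a patient with a known, dated failure and records one censored day. For next therapy this goes against the point of the endpoint: FFS exists to catch patients who change treatment before progression is formally documented, and row 5 drops some of them. The SAP gives no reason for the exception.

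What is at stake is the FFS event count and the Kaplan-Meier summary. SAP 7 tabulates patients with event, P25, median, P75 and patients censored. SAP 6.1 presents data by dose cohort, and the synopsis puts 1 to 6 patients at a dose level, so one recoded patient would show.

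**Working it through.** The documents give no figure to reproduce. The check applies the rows to example patients and then sizes the effect under stated assumptions.

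**1. The cut-off.** Take week 4 as day 22, the fourth infusion of course 1. Consider an unassessed patient who starts next therapy:
- on day 22: definition gives an event at day 22; row 4 gives an event at day 22;
- on day 23: definition gives an event at day 23; row 5 gives censoring at day 1;
- on day 60: definition gives an event at day 60; row 5 gives censoring at day 1.

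The day-1 value comes from the censored-time formula with first administration as the outcome date: 0 + 1 = 1 day. An assessed patient with any of these histories is an event under row 1. Nothing in the definition supports a change of outcome between days 22 and 23.

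**2. Is the event observable without a disease assessment?** Yes for next therapy. Protocol 6.2.3.1 (end of treatment) says: "If the patient receives other therapy for lymphoma, the therapy has to be stated by name and date of first treatment". Protocol 6.2.3.2 (follow-up) lists: "Treatment with any other anti-lymphoma drug (report start date of treatment and therapy"). The date of death is also listed there. SAP 6.6 adds: "If start of new NHL therapy date is incomplete (only month given), then the start date will be imputed with the 1st of month", with an adjustment if that day precedes the end of study medication. The same section does not impute a date with more than the day missing.

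**3. Event rate.** The number affected is not given; assume one. The loss is 1/n: 1/6 = 16.7 percentage points in a cohort of 6, and 1/53 = 1.9 in the approximately 53 patients of protocol 7.6 (41 + 12).

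**4. Kaplan-Meier, n = 6, assumed times.** The lost failure is on day 45, other failures are on days 60, 90 and 120, and two patients are censored on day 180.

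| | By the definition | Under row 5 |
|---|---|---|
| Events | 4/6 = 66.7% | 3/6 = 50.0% |
| S at day 45 | 5/6 = 0.833 | 1.000 |
| S at day 60 | 4/6 = 0.667 | 4/5 = 0.800 |
| S at day 90 | 3/6 = 0.500 | 3/5 = 0.600 |
| S at day 120 | 2/6 = 0.333 | 2/5 = 0.400 |
| P25 | day 60 | day 90 |
| Median | day 90 (105 by midpoint) | day 120 |
| P75 | not reached | not reached |

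If the cohort has no other event, the count goes from 1/6 to 0/6 and the curve ends at 100% instead of 83.3%.

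**5. Direction.** Being censored on day 1 has the same effect as being left out. With no other censoring up to time t and d failures by then, including the lost one, the definition gives (n − d)/n and row 5 gives (n − d)/(n − 1), which is higher unless everyone has failed. Before the lost failure, the values are (n − d)/n and (n − 1 − d)/(n − 1), so the row 5 curve is slightly lower there. The upward shift therefore applies from the lost failure onward.

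**6. Whole trial, assumed.** Take N = 53, exponential times with median 90 days, follow-up cut at day 350, and the earliest failures after day 22 affected. With none affected there are 49 events, the median is 90 days and FFS at day 90 is 49.1%. With one affected: 48 events, 95 days, 50.0%. With five affected: 44 events, 106 days, 54.3%.

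**The case against.** The strongest defence is that this is a convention, not a slip. The week 4 split has its own rows in both the PFS and the FFS table, the protocol delegates censoring to the SAP, and censoring rules often qualify a definition. Without assessments, an earlier progression could go unseen, and dating failure at a later death or therapy could overstate failure-free time. That has some force for PFS. It is weak for FFS: next therapy is itself an event and is seen without an assessment, row 1 already accepts gaps of any length, and day-1 censoring discards the failure altogether.

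The second defence, that the group is close to empty, largely stands. Protocol 3.2 and 6.2.2.1 schedule clinical assessment at the fourth infusion and at the end of course 1, and the flowchart adds one at EOT. A patient must miss all of these, for example by withdrawing early when EOT, required only if feasible (protocol 3.3.4.1), is not done.

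Four stronger readings are tempting, but the documents do not support them:
- That the SAP's censoring sentence rules out row 5. It names patients who will be censored; it does not say that no others will be.
- That the parallel last row of Table 5.2.2:1 is also an error. For PFS it can be a deliberate missed-assessment rule, and changing it would be a choice between conventions.
- That telephone follow-up creates the group. Follow-up visits come after EOT, where an assessment is scheduled, so a telephone contact alone does not leave a patient unassessed.
- That every date needed is available. SAP 6.6 leaves some therapy dates unimputed, and follow-up ends at loss to follow-up or withdrawal of consent.

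**Conclusion.** The point holds for the FFS row only. Row 5 contradicts the FFS definition, the minimum-date formula, row 1 and the stated purpose of the endpoint, and no other passage overrides it.

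Severity is minor. The number affected is unknown and may be zero. It also depends on whether the row heading means that either assessment is missing or that both are; the first reading would widen the group. The rates in step 3 assume one affected patient, and the curves in steps 4 and 6 rest wholly on assumed times. The consequence is confined to exploratory FFS counts and Kaplan-Meier estimates. No formal test is planned, and the MTD, which rests on DLTs, is not affected.

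**What to change.** In Table 5.2.2:2, change the last row to: event, on the date of death or start of next NHL therapy, whichever is first. Merge it with the row above. Keep censoring at first administration only for unassessed patients with neither event.

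Add two clarifications: whether the heading of the unassessed rows means either or both of the baseline and post-baseline assessments missing, and how a next-therapy date that SAP 6.6 does not impute is handled.

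The cost is one table row and two sentences, with no new data collection. Exploratory FFS may look slightly less favourable. Table 5.2.2:1 can stay as it is.
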